9.1. Pharmacokinetic / Pharmacodynamic Analyses

If data permit, exploratory PK/PD analyses for TQ data may be undertaken to examine any relationship between PK parameters (e.g. systemic exposure) and/or clinical outcome (relapse-free efficacy) or safety parameters (e.g. change in MetHb). Similarly, exploratory PK/PD analyses for chloroquine and/or desethylchloroquine data will be undertaken only if safety or efficacy results indicate that these data are needed to understand the PK/PD relationships for TQ. Any exposure-response analyses based on emerging data will be described in detail in the study report. A separate analysis plan will describe the details for the population PK/PD analyses.

10. PHARMACOGENETIC ANALYSES

A summary of the number (and percentage) of subjects who gave Pharmacogenetics consent and the status of the genotype samples and data will be produced for all randomised subjects (Table 5.1) Genetic consent will be further detailed in Table 5.2 (reasons consent not obtained, consent withdrawn, sample destruction) for all randomised subjects. A summary of allele frequency by treatment (Table 5.3) and by treatment and region will also be produced for the Safety population (Table 5.4).

10.1. CYP2D6 Metabolism Status

The effect of CYP2D6 metaboliser class on relapse-free efficacy will be analysed as described in Section [8.1.2](#)

11. OTHER STATISTICAL ANALYSES

11.1. Health Outcomes Analyses

Descriptive summaries of the cost of illness questionnaire will be produced for the Safety population.

The aim of these analyses is to determine the cost of an episode of *P. vivax* malaria and an event of haemolysis (regardless of treatment received in this study).

The costs spent on treatment, transport, medication and tests, together with a total cost, will be summarised according to the place at which the subject went to for care (drug shop, trial clinic, other clinic, hospital (inpatient/outpatient), traditional healer, other). Table 6.1 will present the costs associated with the initial episode of malaria, split by country and by visit (Randomisation, Day 15 (follow-up), overall). Table 6.2 will present the costs associated with a relapse episode of malaria, split by country and by visit. Table 6.3 will present the same information associated with a haemolysis event.

The medications purchased will be summarised by cost and according to whether they were associated with a clinic/healer or hospital. Again these will be split by country and visit for the initial episode of malaria (Table 6.4), a relapse episode of malaria (Table 6.5) and haemolysis events (Table 6.6).

A summary of the time lost due to an episode of malaria will be summarised in days according to the subject's occupation. Again these will be split by country and visit for the initial episode of malaria (Table 6.7), a relapse episode of malaria (Table 6.8) and haemolysis events (Table 6.9).

A summary of what subjects did to treat the illness before attending the trial clinic will be summarised by country and visit for the initial episode of malaria (Table 6.10), a relapse episode of malaria (Table 6.11) and haemolysis events (Table 6.12).

Costs will be presented in the original currency and also in United States dollars (USD) to allow costs to be compared across countries. See Section [13.6.5](#) for conversion to US dollars.

13.1. Appendix 1: Protocol Deviation Management and Definitions for Per Protocol Population

13.1.1. Protocol deviations

Major protocol violations could impact the ability to assess efficacy and our primary endpoints for our study. A subject meeting any of the following criteria will be excluded from the Per Protocol population:

Number	Exclusion Description
1	Subject does not have a parasitology assessment within window for any of the Day 2, Day 3, Day 29, Day 60, Day 90, Day 120, Day 150 or Day 180 visits
2	Subject does not demonstrate initial parasite clearance but does not receive rescue medication
3	When in the clinic on Day 1 to 3, subject vomited a dose of study medication and either vomited the redose, or a redose was not given
4	PQ/PQ placebo pill count suggests that the subject failed to take two or more scheduled doses when away from the clinic
5	Violation of any of the following entry criteria: 
 • Subject had a mixed malaria infection at baseline • Subject had an asexual P. vivax parasite count ≤ 100 or ≥ 100000 • Subject had a severe malaria infection • Subject had severe vomiting or diarrhoea • Subject had taken anti-malarials within the previous 30 days
6	The subject has taken/received: 
 • anti-malarials (e.g., artemisinin-based combination therapies, mefloquine, primaquine, or any other 4- or 8-aminoquinoline) within 30 days prior to study entry. • treatment with any investigational drug within 30 days of study entry, or within 5 half-lives, whichever is longer. • a concomitant medication with an anti-malarial activity between Day 1 and the Day 180 visit, and remained parasite negative throughout the study. A list of all concomitant medications will be reviewed by a GSK clinician prior to unblinding the study, and classified accordingly

NOTES:

- A listing will be produced for the PP population showing
 1. individual subject numbers for each protocol violation
 2. the number and percentage of subjects for each violation
 3. the total number of subjects with one or more violation will be tabulated, by type of violation.

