Analysis Populations	
 Safety Population: all randomized subjects who received at least one dose of blinded study medication. If subjects receive a treatment different to their randomized treatment, they will be analyzed according to the treatment actually received. This will be the primary population for all safety analyses and data presentations. Microbiologic Intent to Treat (mITT) Population: all randomized subjects who receive at least one dose of blinded study medication and have microscopically-confirmed vivax parasitemia. Subjects will be analyzed according to their randomized treatment. This population will be the primary population for all efficacy analyses. Per Protocol (PP) Population: all subjects in the mITT population for whom there were no major protocol violations. This population will be used for sensitivity/supporting analyses of efficacy data only. Ophthalmic Safety Population: all subjects in the safety population who have results from any eye assessments.
Hypothesis	
 There will be no hypotheses tested in this study.

Overview	Key Elements of the RAP
Primary Analyses	
 The proportion of subjects with clinically relevant haemolysis in each treatment group will be presented together with a confidence interval based on the Wilson score. The difference between treatment groups in the proportion of subjects with clinically relevant haemolysis in each treatment group will be presented together with a confidence interval based on the Newcombe method

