13.14.11. Non-ICH Listings

Non-ICH: Listings					
No.	Population	IDSL / TST ID / Example Shell	Title	Programming Notes	Deliverable
Study Population - Subject Disposition					
20.	All Subjects Screened	ES7	Listing of Reasons for Screen Failure	Journal Guidelines	SAC
21.	Safety	TA1	Listing of Planned and Actual Treatments	IDSL	SAC
Study Population - Demographic and Baseline Characteristics					
22.	Safety	LA1	Listing of Malaria Signs and Symptoms at Baseline		SAC
23.	Safety	MH2	Listing of Past and Current Medical Conditions		SAC
Study Population - Concomitant Medication					
24.	Safety	CM2	Listing of Prior and Concomitant Medications	Include concomitant medications and prior medications taken within 30 days of first dose of study medication	SAC
Study Population - Compliance					
25.	Safety	LA7b	Listing of Compliance Data		SAC
Efficacy					
26.	mITT	LA4	Listing of Results of Efficacy Endpoints		SAC
27.	mITT	LA5	Listing of Malarial Parasite Counts		SAC
28.	mITT	LA6	Listing of Time to Fever Clearance Data		SAC
29.	mITT	LA10	Listing of Chloroquine and Desethylchloroquine Concentrations for Subjects who are Early Failures		SAC
Safety - Adverse Events					
30.	Safety	AE2	Listing of Relationship Between Adverse Event System Organ Classes, Preferred Terms and Verbatim Text	IDSL	SAC

Non-ICH: Listings					
No.	Population	IDSL / TST ID / Example Shell	Title	Programming Notes	Deliverable
Safety - All Laboratory endpoints					
31.	Safety	LA8	Listing of Haemoglobin Drops for G6PD Deficient Subjects		
Safety - Hepatobiliary (Liver)					
32.	Safety	LIVER5	Listing of Liver Event Results and Time of Event Relative to Treatment		SAC
33.	Safety	LIVER6	Listing of Liver Event Information for RUCAM Score		SAC
34.	Safety	LIVER8	Listing of Liver Imaging Details		SAC
35.	Safety	LIVER7	Listing of Liver Biopsy Details		SAC
Safety - ECG					
36.	Safety	EG3	Listing of ECG Values		SAC
37.	Safety	EG5	Listing of ECG Findings		SAC
Safety - Ophthalmic Assessments					
38.	Ophthalmic Safety	LA2	Listing of Ophthalmic Assessments		SAC
39.	Ophthalmic Safety	LA3	Listing of Retinal Examination		SAC
Health Outcomes – Cost of Illness Survey					
40.	Safety	LA9	Listing of Cost of Illness Survey		SAC

CONFIDENTIAL

The GlaxoSmithKline group of companies

TAF116564

Division	: Worldwide Development
Information Type	: Reporting and Analysis Plan (RAP)

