5. ANALYSIS POPULATIONS

Microbiologic Intent to Treat (mITT) Population: all randomized subjects who receive at least one dose of blinded study medication and have microscopically-confirmed *P. vivax* parasitemia. Subjects will be analyzed according to their randomized treatment.

Per Protocol (PP) Population: all subjects in the mITT population for whom there were no major protocol violations within the individual studies.

The PP population will be the primary population for the non-inferiority analysis and the mITT population will be used for sensitivity/supporting analysis.

The rationale behind looking at both the mITT and PP populations is that we want to be able to claim superiority, if it exists. The PP population is considered more conservative for non-inferiority analysis, where any existing treatment differences are not underestimated due to the presence of protocol violators. Conversely, the the mITT population is considered more conservative for a superiority analysis, so we are stating up-front an intention to look at both.

The datasets will contain flags to identify which analysis populations subjects are eligible for. Inclusion in the mITT and PP populations was determined for individual patients within the DETECTIVE Part 2 and GATHER studies prior to the unblinding of the studies. The populations used for this meta-analysis will be consistent with the studies, and details of major protocol violations resulting in exclusion from the PP population are provided in the study reporting and analysis plans.

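### The closed Per Protocol exclusion list has no criterion for receiving a treatment other than the one randomised, nor for an in-clinic dose omitted or partly given without vomiting

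*Supplement*

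**What the plan says.** RAP Section 13.1.1 (amendment 1) introduces its list with "A subject meeting any of the following criteria will be excluded from the Per Protocol population". The six items are:

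1. missing parasitology at named visits
2. no initial clearance and no rescue medication
3. an in-clinic dose lost to vomiting, worded as "subject vomited a dose of study medication and either vomited the redose, or a redose was not given"
4. an outpatient PQ/placebo count that is short by at least two doses
5. selected entry-criteria violations
6. anti-malarial or investigational drugs

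For the Safety population the RAP provides for treatment mismatches: "If subjects receive a treatment different to their randomized treatment, they will be analyzed according to the treatment actually received". Listing 21 is a "Listing of Planned and Actual Treatments".

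Within GATHER the PP population is secondary: "This population will be used for sensitivity/supporting analyses of efficacy data only". The Meta-Analysis Plan, Section 5, gives it a larger role: "The PP population will be the primary population for the non-inferiority analysis". That section refers to the study RAPs for the violations that remove a subject from PP. Its stated reason for preferring PP is that violators should not cause a treatment difference to be understated. For the mITT population it says "Subjects will be analyzed according to their randomized treatment", and it does not repeat this for PP.

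**The concern.** Receiving the assigned treatment is the most basic condition for a per-protocol set, and it is absent here. A subject given the other arm's drug meets none of the six criteria.

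The in-clinic gap falls mainly on TQ, which is one two-tablet dose given on Day 1 or 2 (Protocol 5.1.8). If that dose is omitted or halved and nothing is vomited, criterion 3 does not apply. Criterion 4 concerns only PQ/placebo taken away from the clinic. The compliance rule in RAP 13.6.2 does not close the gap, because it asks whether the subject kept down what was given, not whether the full dose was given. Nor does mITT membership close it. One dose of any blinded medication suffices, and Protocol 5.1 counts PQ placebo as blinded medication.

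In a non-inferiority comparison, subjects analysed in one arm but treated as in the other make the arms look alike. The Meta-Analysis Plan chose PP to avoid that.

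**Working it through.** **Inputs from the Meta-Analysis Plan.**
- Section 9.1: CQ only versus PQ+CQ hazard ratio 3.68 (1.84 to 7.35); 75% of the effect preserved; margin 1.21; 428 TQ+CQ and 214 PQ+CQ subjects expected.
- Section 9.3: 12/40 = 30% relapse on PQ+CQ.
- Section 3: 522 subjects in DETECTIVE Part 2 (2:1:1) and 251 in GATHER (2:1).
- The documents give no frequency of wrong or incomplete treatment, so every such share below is an assumption.

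**The plan's own figures.**
- Margin: 1 + (1 − 0.75) × (1.84 − 1) = 1.21.
- Numbers: 522/2 + 251 × 2/3 = 428.3, and 522/4 + 251/3 = 214.2. Both agree with the plan.

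**Model.** With 30% relapse on PQ, the six-month cumulative hazards are:
- PQ: −ln(0.70) = 0.3567
- TQ at the margin: 1.21 × 0.3567 = 0.4316
- CQ only: 3.68 × 0.3567 = 1.3126

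The corresponding relapse-free proportions are 0.700, 0.6495 and 0.2691. A swapped subject takes the other arm's hazard. An under-dosed subject is given the CQ-only hazard, which is the extreme case. Everyone is analysed as randomised. Observed HR = ln(S_TQ, mixed) / ln(S_PQ, mixed).

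**Example, 2% swapped in each arm.**
- S_TQ = 0.98 × 0.6495 + 0.02 × 0.700 = 0.6505
- S_PQ = 0.98 × 0.700 + 0.02 × 0.6495 = 0.6990
- HR = 0.4300/0.3581 = 1.201
- Expected events: 428 × 0.3495 = 149.6 and 214 × 0.3010 = 64.4
- SE = √(1/149.6 + 1/64.4) = 0.149
- False non-inferiority rate = Φ(−1.96 + [ln 1.21 − ln 1.201]/0.149) ≈ 2.8%

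**All cases at a true HR of 1.21.**

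| Assumed share left in PP | Observed HR | False non-inferiority |
|---|---|---|
| none | 1.210 | 2.5% |
| 1% swapped, both arms | 1.205 | 2.7% |
| 2% swapped, both arms | 1.201 | 2.8% |
| 5% swapped, both arms | 1.187 | 3.4% |
| 10% swapped, both arms | 1.165 | 4.4% |
| 5% swapped in GATHER only | 1.201 | 2.8% |
| 5% untreated, TQ arm only | 1.293 | 0.8% |
| 5% untreated, PQ arm only | 1.112 | 8.3% |
| 5% untreated, both arms | 1.189 | 3.3% |

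The GATHER-only row is 0.05 × 251 ≈ 13 subjects, and 0.05 × 251/642.5 ≈ 2.0% overall. If PQ relapse is taken as 20% or 40% instead of 30%, the 2% swap still gives 1.201, with an error of 2.8% to 2.9%.

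The PQ-only row is not a realistic size for this gap. By the Protocol 5.1.8 schedule, only two or three of the 14 PQ doses fall within the three-day hospital stay, and criterion 4 already handles the outpatient doses. A PQ subject caught by this gap is therefore far from untreated. The TQ-only row is closer to what an omission means, because the single dose is the whole treatment.

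**The case against.** A reader might infer that the list ignores incomplete dosing altogether. It does not: criteria 3 and 4 address it, and only doses missed in clinic without vomiting fall between them.

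A reader might also infer that the gap always helps non-inferiority. That holds for swaps and for similar under-dosing in both arms. Missing TQ moves the ratio the other way, from 1.21 to 1.29 in the table. Excluding such subjects would lower the ratio and make non-inferiority easier to show, so that part of the repair is not conservative. It rests on what per protocol means, and the supporting mITT analysis still keeps those subjects.

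Third, analysis of PP by randomised arm is inferred from PP being a subset of mITT. RAP 13.5.3 makes actual treatment the default unless Section 4 says otherwise, and the PP row in Section 4 is silent. If PP were analysed as treated, a complete swap would not dilute the contrast. This objection stands, and it is a reason to state the rule.

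Fourth, the list governs only GATHER, about 39% of the pooled subjects (251/642.5). GATHER itself tests no hypothesis. Central allocation, matching placebos and observed dosing on Days 1 to 3 make errors unlikely. Deviations are also tracked under a management plan that is not shown. All of this limits the size. It does not supply the missing criterion, because RAP 4.1 refers to Appendix 1 for exclusions.

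**Conclusion.** The omission is real and minor. The list has no wrong-treatment criterion and does not cover an in-clinic dose omitted or partly given without vomiting. Swapped subjects kept under their randomised arm would work against the Meta-Analysis Plan's own reason for making PP primary. The plausible cost is a false non-inferiority rate of about 2.8% instead of 2.5%, at an assumed 2% overall swap rate.

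That figure rests on 30% PQ relapse, the planned numbers, a normal approximation and randomised-arm analysis of PP. For under-dosing no single direction can be claimed. The documents do not support a claim that the non-inferiority result is materially threatened, or that DETECTIVE Part 2 shares the gap, since its plan is not shown.

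**What to change.** Before unblinding, amend RAP 13.1.1 for both arms:

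- Exclude a subject who did not receive the randomised blinded treatment.
- Exclude a subject who did not receive the full single TQ/TQ placebo dose, whether or not vomiting occurred.
- Count missed in-clinic PQ/PQ placebo doses together with outpatient ones toward the threshold of two in criterion 4, so that the same missed dose is not judged differently by place.

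In Section 4, state that PP is analysed by randomised treatment. For swaps this becomes moot once they are excluded. Check the DETECTIVE Part 2 plan for the same items and align it if needed.

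The cost is a few lines of text. Listing 21 already calls for planned and actual treatment, and dosing is recorded. A few subjects may leave PP, and the estimate is expected to change little.

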3. The subject has a screening hemoglobin (Hb) value as follows:
 - Any subject with a G6PD value $\geq 70\%$ of the site median value must have a screening Hb value ≥ 7 g/dL.
 - Female subjects with a G6PD value is $\geq 40\%$ - <70% of the site median value must have a screening Hb value ≥ 8 g/dL.

4. The subject has a QTcF of <450 msec.

N.B. Reading based on an average of triplicate ECGs obtained over a brief recording period by machine or manual over-read.

Efficacy

5. The subject has a positive malarial smear for *P. vivax*.
6. The subject has a parasite density of >100 and <100,000/ μ L.

Other

7. Male or female subject aged 16 years or older (18 years or older in Ethiopia) at the time of signing the informed consent.
8. The subject agrees to G6PD genotyping.
9. The subject is willing and able to comply with the study protocol.
10. The subject or parent/legal guardian, as applicable, has given written informed, dated consent; and the subject has given written assent, if applicable, to participate in the study.

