Pharmacokinetic Assessments																
PK/PD Sampling ^u		X	X		X		X		X	X					X	
Investigational Product																
Dispense Open Label Chloroquine	X	X	X													
Dispense Blinded Study Medication	X ^v	X ^v														
Treatment Compliance Int. - Invest.	X	X	X	X	X	X	X									
IVRS Registration	X															

- a All subjects must remain hospitalized for Days 1 through 3.
- b Subjects who relapse will continue to be monitored for safety and efficacy at all scheduled visits through day 180. Relapse is defined by a positive blood smear with or without vivax symptoms.
- c If subjects withdraw from blinded study medication, all scheduled follow-up visits should be performed to conduct safety assessments up to and including Day 180.
- d Visit Day 1 includes all screening procedures and the first day of treatment with study medication.
- e Includes medical, disease and therapy histories.
- f Blood smears are to be taken twice a day, 6-12 hours apart for the first 3 days, or until 2 consecutive negative thick blood smears are obtained.
- g Vital signs include height and weight (screening only), blood pressure, temperature, heart rate and respiratory rate. Vital signs are to be performed twice a day on Days 1 through 3, at least 4 hours apart, and immediately prior to PK measurements.
- h ECGs are to be performed at screening (in triplicate), 12 hours after the first dose of blinded study medication, and on Day 29.
- i Adverse events are recorded from the time of the first dose of study medication.
- j Serious adverse events are recorded from the time of consent in order to fulfil international regulatory requirements.
- k G6PD phenotyping to be performed by quantitative spectrophotometric analysis. One or more G6PD rapid point of care tests may be performed at baseline (Day 1) only.
- l Only if Day 90 ophthalmological exam shows abnormalities.
- m Hematology includes hemoglobin, hematocrit, red blood cell/white blood cell/platelet counts, mean cell volume, white blood cell differential and reticulocyte count.

- n Hematology and clinical chemistry on Day 3 must be reviewed prior to discharge from the hospital.
- o Clinical Chemistry includes CPK, BUN, serum creatinine, total and indirect bilirubin and liver clinical chemistry.
- p Mid-stream urine will be analyzed for protein, glucose, ketones, bilirubin, blood, nitrites, urobilinogen and leukocyte esterase by dipstick method.

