Subjects who have one or more visits outside the allowable time window defined for each scheduled visit (see [Table 2](#)) will undergo all the procedures and assessments described in [Table 2](#) with the exception of assessments performed only at screening and the PK assessments. Subjects should be able and/or encouraged to return to the clinic for unscheduled visits at anytime during the 180-day study period. **In addition, subjects must return to the clinic anytime they are experiencing a recurrence of malaria symptoms.**

6.3. **Efficacy**

Parasitology

Asexual parasite counts:

Microscope blood slides will be prepared pre-dose at screening on Day 1, post-dose on Day 1, then twice a day, 6-12 hours apart for the first 3 days, or until 2 consecutive negative thick blood smears are obtained. Where the subject receives CQ <6 hours from midnight on day 1, a post dose slide can be taken early on day 2. Microscope blood slides will be prepared at subsequent visits on Days 8, 15, 22, 29, 60, 90, 120, 150 and 180. In addition, blood films should be obtained whenever parasitological re-assessment is required and at the relapse visit or withdrawal visit as applicable. At each time point two thick and one thin film slide should be prepared on separate slides and one additional unstained slide with both thick and thin films retained for quality control. For detailed instructions on the methodology for staining and counting please refer to the SPM.

In summary:

Thick film parasitemia (malaria parasite density) should be calculated first, using the subjects' actual white blood cell count (WBC). Aim to count the number of parasites per 200-250 WBCs:

$$\text{i.e., D1 parasitemia}/\mu\text{L} = (\text{number of D1 parasites}/\text{D1 WBC counted}) \times \text{D1 WBC count}$$

If after 200 WBCs have been counted, 9 or fewer parasites have been identified, continue counting until reaching 500 WBCs.

If the thick film contains > 250 asexual parasites per 50 WBC (i.e. 5 parasites per WBC, equivalent to 40,000 asexual parasites/ μL), 8 high power fields on the thin film should be

read and parasites counted against (assuming 250 RBC per high powered field = 2000) red blood cells counted (RBCs).

Parasitemia from thin films is then calculated as:

$$\text{Parasitemia}/\mu\text{L} = (\text{number of parasites in 8 high powered fields} / \text{RBC counted} = 2000) \times 4,000,000 [\text{assumed RBC}]$$

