The calculated parasitemia/ μL will be recorded into the eCRF for each time point. See SPM for quality control procedures.

Local quality control of slides is performed by reading of the slide by 2 different qualified microscopists. If the results from the two readings are within 20% of each other for the parasite count and the two readers agree on the species identification then the average result from the two microscopists is computed and recorded in the eCRF.

If the results from the two microscopists are different by more than 20 % or they disagree on the species identification then a third independent reader is required who will read both slides. The average count from the third independent reader is compared with results from the first two readers. The count of the first two readers closest to the average count of the third independent reader is regarded as final and should be recorded in the eCRF. The third reader should therefore be a highly experienced malaria microscopist.

Slides are considered negative after review of 100 high-power fields.

Gametocyte counts

In the same way, thick film slides will be read for gametocytes on Day 1 (pre-dose and post-dose) and then twice daily for the remainder of the in-patient stay. Slides will be prepared at subsequent visits on Days 8, 15, 22, 29, 60, 90, 120, 150 and 180 (and relapse and withdrawal visits if applicable). If gametocytes are present they will be counted against a 200-250 WBCs and their density calculated as follows:

$$\text{Gametocytes}/\mu\text{L} = (\text{number of gametocytes}/\text{WBC counted}) \times \text{WBC count}$$

Parasite Genotyping

Two drops of peripheral blood will be collected onto pre-printed filter paper for subsequent DNA extraction and PCR analysis of *Plasmodium* species on all subjects at screening (Day 1; pre-dose) and; if necessary, at the time of the first recrudescence/relapse or re-infection.

PCR of the *P. vivax* genes, such as *PvMSP-1*, *PvCSP* and *PvAMA-1*, as well as any other markers deemed appropriate, will be used to distinguish between genetically homologous and genetically heterologous infection.

Parasite whole genome sequencing

Four milliliters of blood will be taken for subsequent parasite exploratory whole genome sequencing at baseline and at the relapse visit. If the time taken to transport samples to

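### The Per Protocol rule has no exemption for a missing Day 3 smear after clearance, although the smear schedule can be read as letting smears stop once two are negative

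*Supplement*

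**What the plan says.** RAP 13.1.1 lists the PP exclusions. Item 1 reads "Subject does not have a parasitology assessment within window for any of the Day 2, Day 3, Day 29" and goes on through the visits to Day 180. It has no clause for subjects who have already cleared.

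Protocol Amendment 5, Table 2, marks a smear on Days 1, 2 and 3 and qualifies each with footnote f: smears twice a day, "6-12 hours apart for the first 3 days, or until 2 consecutive negative thick blood smears are obtained". Protocol 3.2 and 6.3 use the same construction, and the RAP reprints the footnote in 13.2.1. The next scheduled smear after Day 3 is on Day 8.

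Two other protocol statements bear on Day 3. Table 2 footnote a says "All subjects must remain hospitalized for Days 1 through 3". Section 6.3 says thick films are read for gametocytes on Day 1 "and then twice daily for the remainder of the in-patient stay".

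RAP 13.7.2.3 also describes PP exclusion for missing smears, but only from the Day 29 assessment onwards. It does not mention Day 2 or Day 3.

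PP is supportive in this trial (RAP section 4). In section 5 of the Meta-Analysis Plan, which uses the study-level PP flags, "The PP population will be the primary population for the non-inferiority analysis".

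**The concern.** If footnote f means whichever comes first, a site may stop asexual smears once a subject has two consecutive negatives. Item 1 would then class that subject as a major protocol violator for a smear the schedule did not require. The exclusion would depend on how fast parasites cleared, which is a post-randomisation outcome and not a measure of adherence.

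The missing smear also carries no information the analysis needs. RAP 13.6.4 defines initial clearance, and parasite clearance time, by two negative asexual counts at least 6 hours apart with no positive count between them. A subject who has those is evaluable without a Day 3 smear.

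At stake are the precision and composition of the PP set, chiefly where it is the primary population for testing tafenoquine against primaquine at a hazard-ratio margin of 1.21 (Meta-Analysis Plan 9.1 and 9.4).

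**Working it through.** The plan gives no figure for this point, so there is nothing to reproduce. The check has two parts.

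**1. Which day can a fast clearer lack?**

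- Inclusion criterion 5: "The subject has a positive malarial smear for" *P. vivax*. The pre-dose Day 1 smear therefore cannot be one of the two negatives.
- Protocol 6.3: "Microscope blood slides will be prepared pre-dose at screening on Day 1, post-dose on Day 1, then twice a day, 6-12 hours apart". Only one post-dose smear is scheduled on Day 1, and it may slip to early Day 2 when chloroquine is given late on Day 1.
- The earliest scheduled pair of consecutive negatives is therefore the Day 1 post-dose smear plus the first Day 2 smear. On the scheduled smears, every fast clearer has a Day 2 smear, so Day 2 is not affected.
- A subject with two negatives by the end of Day 2 has none due on Day 3 if footnote f permits stopping. The RAP's Day 3 window is Study Days 3 to 4 (13.3.1) and the next scheduled smear is Day 8, so the window can be empty and item 1 then excludes the subject.

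**2. What would the loss cost?**

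Inputs: 251 subjects randomised here (Meta-Analysis Plan, section 3) and about 642 expected in the pooled comparison (section 9.1). The fraction f of this trial's subjects lost for this reason is not in the documents, so 10%, 25% and 40% are assumed. Information is taken as proportional to subjects, and the pooled column assumes that only this trial is affected.

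- This trial's PP set: SE ratio = 1/√(1 − f)
- Pooled analysis: SE ratio = √(642/(642 − 251f))

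| f (assumed) | Subjects lost (251f) | SE ratio, this trial | SE ratio, pooled |
|---|---|---|---|
| 10% | 25.1 | 1/√0.90 = 1.05 | √(642/616.9) = 1.02 |
| 25% | 62.8 | 1/√0.75 = 1.15 | √(642/579.2) = 1.05 |
| 40% | 100.4 | 1/√0.60 = 1.29 | √(642/541.6) = 1.09 |

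If every subject had a Day 3 thick film that counts as a parasitology assessment, f = 0 and both ratios are 1.00.

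**The case against.** The strongest reply is that nobody may be affected. All subjects are in hospital through Day 3, and section 6.3 has thick films read for gametocytes twice daily throughout the stay, with no stop at asexual clearance. Item 1 asks for a parasitology assessment, not specifically an asexual count. Protocol 3.3 applies the same two-negatives wording to a hospital stay whose minimum is three days, so there it can only mean an extension. Section 3.2 likewise lengthens the stay when two negatives are not obtained in time. This stands as a reason not to assert that exclusions occur. It does not settle the matter, because nothing says which reading governs footnote f or whether a gametocyte reading satisfies item 1.

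A reader might infer that the rule selects differently by arm, since the protocol describes tafenoquine as active against all parasite stages. The documents do not support that. Both arms receive the same chloroquine from Day 1, blinded drug starts on Day 1 or 2, and the only clearance comparison cited (protocol 3.3.1) reports tafenoquine monotherapy as slower than chloroquine plus primaquine.

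Two further replies have weight. PP is only supportive in this trial, and the meta-analysis also analyses mITT. Changing item 1 here alone could also make this trial's PP definition differ from that of the sister study, whose analysis plan is not among these documents.

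**Conclusion.** The point holds as a gap in the PP rule, confined to Day 3. Item 1 has no exemption for subjects already cleared, footnote f can be read as permitting the missing smear, and RAP 13.7.2.3 states the smear requirement only from Day 29. Subjects who cleared by the end of Day 2 can therefore be excluded although managed as the footnote allows.

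The documents do not show that any subject is excluded this way, and they show no imbalance between arms. The precision figures are illustrations at assumed losses. They are also rough, because the precision of a Cox model follows relapse events more closely than headcount. In the pooled analysis, where PP matters most, the cost is modest even at a 40% loss in this trial. The correction is worth making because it is cheap and keeps speed of clearance from deciding membership of a primary non-inferiority population.

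**What to change.** Before unblinding:

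1. Amend RAP 13.1.1 item 1 so that a missing Day 3 smear excludes a subject only if two consecutive negative asexual counts, at least 6 hours apart, were not already recorded. Leave the Day 29 to Day 180 part unchanged.
2. State whether a Day 3 gametocyte slide satisfies item 1.
3. Reconcile item 1 with footnote f, the gametocyte paragraph of protocol 6.3 and RAP 13.7.2.3, so that one reading governs.
4. Apply the same rule to the sister study's PP flag, so that the pooled PP definition stays uniform.

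The cost is one clause, one clarifying sentence, a re-run of the PP flag and agreement with the sister study's team. If no subject lacks a Day 3 smear, no result changes.
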